#### Malignancies

- In case of occurrence of malignant neoplasm other than appropriately treated basal cell carcinoma or squamous cell carcinoma of the skin or in situ carcinoma of uterine cervix, the investigator should discontinue treatment with study drug. Diagnostics and treatment have to be initiated according to local standard of care.

## 4.2.2 Restrictions

4.2.2.1 Restrictions regarding previous and concomitant treatment are summarized in Table 4.2.2.1: 1

Table 4.2.2.1: 1 Restrictions regarding previous and concomitant treatment

Medication or class of medications	Restriction
any biologic approved for UC adalimumab, infliximab, golimumab, vedolizumab	Not allowed from 8 weeks prior to randomisation or from time when no detectable drug level was confirmed until end of the trial For use as rescue medication, refer to Section 4.2.1
any investigational or non-approved biologic for UC (incl. ustekinumab, other IL-23 inhibitors, etrolizumab, certolizumab)	not allowed from 8 weeks prior to randomisation or when negative drug level is detected before randomization until end of the trial For use as rescue medication, refer to Section 4.2.1 .
Any prior treatment with a dose of Ustekinumab approved for UC only applicable where locally approved and available	Any prior exposure is prohibited
Any non-biologic immunomodulator, other than those allowed per inclusion criteria #6 (incl. cyclosporine, tofacitinib and other JAK inhibitors, tacrolimus, sirolimus, mycophenolate mofetile)	Not allowed from 30 days prior to randomisation until end of the trial For use as rescue medication, refer to Section 4.2.1 .
Any immunomodulator allowed per inclusion criteria #6 (Azathioprine, 6-mercaptopurine or methotrexate)	Only allowed during the trial, if dose is stable for at least 8 weeks prior to randomisation until end of the trial For use as rescue medication, refer to Section 4.2.1 .
Any biologic for treatment for any other indication ( e.g. Dupilumab for the treatment of atopic dermatitis)	Not allowed from 8 weeks prior to randomisation until end of the trial
Fecal microbiota transplantation (FMT)	Not allowed from 30 days prior to randomisation until end of the trial
BI655130 (SPESOLIMAB), natalizumab or rituximab	Any prior exposure is prohibited
5-ASA	Oral administration: Only allowed during the trial, if dose is stable for at least 4 weeks prior to randomisation until end of the trial Rectal route of administration (5-ASA): Not allowed from 2 weeks prior to screening up to end of the trial For use as rescue medication, refer to Section 4.2.1 .

Table 4.2.2.1: 1 Restrictions regarding previous and concomitant treatment (cont.)

Medication or class of medications	Restriction
Corticosteroids (incl. budesonide)	
Oral administration:
 
Oral steroids are only allowed if indicated for treatment of UC and at a dose of <math>\leq 20</math>mg per day of prednisone or equivalent and with stable dose for at least 2 weeks prior to randomisation and throughout the trial.
 
Short (<7 days) decrease of dose for treatment of AEs with subsequent increase back to initial baseline dose level is allowed
 
Oral budesonide (<math>\leq 9</math> mg per day), provided that dose has been stable for the 2 weeks immediately prior to randomisation
 
Oral beclomethasone dipropionate (<math>\leq 5</math> mg per day), provided that dose has been stable for the 2 weeks immediately prior to randomisation
 
Parenteral administration:
 
Not allowed from 2 weeks prior to screening up to end of the trial.
 
Note: parenteral steroids dosed for less than 24hours as treatment of infusion or anaphylactic reactions are permitted.
 
Rectal administration:
 
Not allowed from 2 weeks prior to screening up to end of the trial
 
Note: steroids will be tapered (or discontinued for budesonide) in subsequent maintenance trial.
 
For use of steroids as rescue medication, refer to Section 4.2.1.
 
Allowed steroid treatments:
 
Short-term use (<7 days) of systemic (oral or parenteral) corticosteroids is allowed for treatment of AE not related to the underlying UC from 4 weeks prior to randomisation until end of the trial.
 
Locally administered steroids as e.g. intra-articular, nasal inhalation or intra-ocular administration are allowed.

NSAID	
Chronic use (i.e. daily use for >2 weeks) not allowed from 2 weeks prior to screening up to end of the trial
 
(Note: occasional use of NSAIDs and acetaminophen for headache, arthritis, myalgias, menstrual cramps, etc., and daily use of baby or low dose (81-162.5mg) aspirin for cardiovascular prophylaxis are permitted.)

Probiotics	
Only allowed during the trial, if dose is stable for at least 4 weeks prior to randomisation until end of the trial

Live ofattenuated vaccines	
Not allowed from 6 weeks prior to screening up to end of the trial

Antibiotics for IBD	
Not allowed from 4 weeks prior to screening up to end of the trial

#### 4.2.2.2 Restrictions regarding women of childbearing potential

Women of childbearing potential must use the contraception methods described below. This information is provided to the patients in the patient information.

Highly effective methods of birth control for female participants.

- Combined (estrogen and progestogen containing) hormonal birth control associated with inhibition of ovulation.
- Progestogen-only hormonal birth control associated with inhibition of ovulation.
- Intrauterine device (IUD) and intrauterine hormone-releasing system (IUS).
- Tubal occlusion (blocking of the fallopian tubes).
- Vasectomy of sexual partner (proven effective by absence of sperm on the ejaculation).
- True abstinence: When this is in line with the preferred and usual lifestyle of the subject. Periodic abstinence (e.g., calendar, ovulation, symptothermal, postovulation methods), declaration of abstinence for the duration of exposure to IMP, and withdrawal are not acceptable methods of contraception.

### 4.3 TREATMENT COMPLIANCE

Study medication will be administered in accordance with the protocol, under supervision of the investigating physician or a designee at the site. Any missed dose has to be documented and reported to the CT Manager.

## 5. ASSESSMENTS

### 5.1 ASSESSMENT OF EFFICACY

The changes in UC activity during the trial will be assessed at visits including endoscopies using the modified Mayo score (disease activity score, not including the PGA (physician global assessment) item, but including the modified ESS (any degree of friability defines a score of at least 2), and the Roberts histopathology index (RHI). In addition, the total Mayo score (including PGA in addition to modified Mayo Score) will be explored as secondary endpoint to facilitate indirect comparisons against currently approved or investigational drugs. At all visits, the partial MCS (pMCS; all subscores except mESS) will be recorded to assess clinical disease activity.

Mucosal healing will be assessed by endoscopy using a blinded central reader and will be defined as a mESS  $\leq$  1. Local reading will be recorded for exploratory reasons, and to be used for endpoint assessment if central reading is not available for technical reasons.

Please refer to [Appendix 10.1](#) (Mayo Score/modified Mayo score) and to [Appendix 10.2](#) (Roberts histopathology index) for further details.

### 5.2 ASSESSMENT OF SAFETY

Safety will be assessed descriptively based on:

- Adverse events
- Serious adverse events (SAEs)
- Clinical laboratory values (haematology, clinical chemistry, coagulation and urinalysis)
- Intensity of adverse events will be assessed by Rheumatology Common Toxicity Criteria (RCTC) version 2.0 (refer to ISF for details)
- Physical examination
- Vital signs
- 12-lead ECG

#### 5.2.1 Physical examination

Complete physical examination will include vital sign assessment and general appearance as well as evaluation of all organ systems. Targeted physical examination will include vital sign assessment and evaluation of organ systems associated with AE(s) symptoms or laboratory abnormalities.

Clinically relevant abnormal findings will be reported as baseline conditions or AEs.

### 5.2.2 Vital signs

Vital signs evaluations will be performed at visits as shown in the [Flow Chart](#). This includes temperature, pulse rate, systolic/diastolic blood pressure and respiratory rate. Respiratory rate, pulse rate, and blood pressure will be measured after patients have been sitting comfortably for at least five minutes. Measurement of vital signs should precede blood sampling to avoid the impact of blood sampling on the vital measurements. At dosing visits (Visits 2, 4 and 5) vital signs evaluations will be performed pre-dose and additional evaluations will be taken approximately at 5 minutes post-dose and 60 minutes post-dose.

Patients should be closely monitored for signs and symptoms of hypersensitivity reactions for approximately 2 hours after the first dose administered and 1 hour following all other doses of study drug. Hypersensitivity reactions should be treated according to medical standards. Pre-medications for further injections might be considered and will be agreed on between investigator and BI clinical monitor.

### 5.2.3 Safety laboratory parameters

Safety laboratory parameters to be assessed are listed in [Table 5.2.3:1](#). For the sampling time points please see the flowchart.

All analyses will be performed by a central laboratory, the respective reference ranges will be provided in the ISF. A local laboratory may be used for selected tests in exceptional cases. Patients should be fasting for at least 8 hours prior to the blood sample being taken (except screening visit).

Instructions regarding sample collection, sample handling/ processing and sample shipping are provided in the Laboratory Manual in the ISF.

The central laboratory will send reports to the investigator. It is the responsibility of the investigator to evaluate the laboratory reports. Clinically relevant abnormal findings as judged by the investigator will be reported as adverse events (please refer to [Section 5.2.6](#)). Laboratory results (i.e. all safety laboratory and clinical laboratory data relevant for current clinical practice) of the patients will be available in real time to the respective investigator (via laboratory reports) and to the sponsor (via the central laboratory website) and selected abnormal laboratory alerts will be flagged to the site and sent to sponsor in real time.

Clinically relevant abnormal findings will be reported as baseline conditions or AEs. A clinically relevant value may be either in- or outside the reference range. Clinically relevant abnormal laboratory test results must be confirmed using an unscheduled visit laboratory kit and should be repeated until normalization or stabilization or until an alternative explanation has been found. Abnormal laboratory values will be also graded for intensity by using RCTC Version 2.0 criteria [[R13-3515](#)].

In case the criteria for hepatic injury are fulfilled, a number of additional measures will be performed (please see [Section 5.2.6.1](#) and the DILI Checklist provided in the ISF EDC system. The amount of blood taken from the patient concerned will be increased due to this additional sampling.

Table 5.2.3: 1 Exclusionary testing

Category	Test name
Infections screening (only at screening)	Hepatitis B Surface Antigen (qualitative) Hepatitis B core Antibody HBV-DNA (quantitative, PCR)  Hepatitis C Antibodies (qualitative) HIV-1, and HIV-2 Antibody (qualitative)
TB screening	QuantiFERON®-TB 
Serum Pregnancy test (only for female patients of childbearing potential)	Human Serum Chorionic Gonadotropin
Stool studies to evaluate for enteric pathogens	Salmonella Shigella Yersinia Campylobacter Vibrio E. coli O157/H7 Clostridia difficile toxin Enteric parasites and their ova (including Cryptosporidia)

 At screening only (visit 1)

 A HBV-DNA should be conducted if Hepatitis B core Antibody is positive and Hepatitis B Surface Antigen is negative (definition of occult HBV infection: B core Antibody is positive, Hepatitis B Surface Antigen is negative; HBV DNA detectable).

 There is the trial site option to perform a PPD skin test

 If the 1st QuantiFERON®-TB test result is undetermined, a re-test should be performed. If the retest QuantiFERON-TB test result is undetermined, a PPD skin test should be performed. This applies for QuantiFERON®-TB test at screening as well as at EOS visit.

Table 5.2.3: 2 Laboratory tests

Category	Test name
Haematology	Hematocrit (Hct) Hemoglobin (Hb) Glycosylated Hbc (HbA1c) (only at screening) Red Blood Cell Count/ Erythrocytes Reticulocyte Count White Blood Cells / Leukocytes Platelet Count/ Thrombocytes
Diff. Automatic	Neutrophils (relative and absolute count) Eosinophils (relative and absolute count) Basophils (relative and absolute count) Monocytes (relative and absolute count) Lymphocytes (relative and absolute count)
Diff. Manual (if Diff Automatic is abnormal)	Neutrophils, bands (Stabs) Neutrophils, polymorphonuclear (PMN) Eosinophils Basophils Monocytes Lymphocytes
Coagulation	Activated Partial Thromboplastin Time (aPTT) Prothrombin time (INR) Fibrinogen
Enzymes	AST (GOT) ALT (GPT) Alkaline Phosphatase (AP) Creatine Kinase (CK) CK-MB, only if CK is elevated Gamma-Glutamyl Transferase (GGT/γ-GT) Lactic Dehydrogenase (LDH) Amylase Lipase
Electrolytes	Calcium Sodium Potassium Chloride Bicarbonate
Substrates	Glucose BUN (blood urea nitrogen) Uric acid Creatinine eGFR (estimated by CKD-EPI formula) (only at screening) Bilirubin Total Bilirubin Direct (if total is elevated) Bilirubin Indirect (if total is elevated) Troponin (Reflex, in case of elevated CK) Protein, Total Albumin C-Reactive Protein (CRP) (high sensitivity) Cholesterol, total Triglycerides LDL-Cholesterol HDL-Cholesterol

Table 5.2.3: 2 Laboratory tests (cont.)

Category	Test name
Specific gamma-globulin quantification	IgE  , IgG
Urine Pregnancy test (only for female patients of childbearing potential)	Human Chorionic Gonadotropin in urine
Serum Pregnancy test (only for female patients of childbearing potential if urine pregnancy test is positive)	Human Serum Chorionic Gonadotropin
Hormones (only at screening)	TSH (free T3 and free T4 in case of abnormal TSH result)
Urinalysis (dipstick)	Urine Nitrite Urine Protein Urine Glucose Urine Ketone Urobilinogen Urine Bilirubin Urine RBC/ Erythrocytes Urine WBC/ Leukocytes Urine pH
Urine-Sediment (microscopic examination, only if urine analysis abnormal)	Urine Sediment Bacteria Urine Cast in Sediment Urine Squamous Epithelial Cells Urine Sed. Crys., Unspecified Urine Sediment RBC/ Erythrocytes Urine Sediment WBC/ Leucocytes
Urine (only at screening)	Albumin (quantitative)
Faecal sample	Calprotectin Lactoferrin
Infections screening	HBV-DNA (quantitative) EOT Visit 
QuantiFERON-TB test	QuantiFERON®-TB 

 Only in case of allergic reaction

 HBV-DNA in case of occult HBV infection (for definition see [Table 5.2.3: 1](#) footnote 2)

 There is the trial site option to perform a PPD skin test instead, if Quantiferon testing is not feasible

 If the 1st QuantiFERON®-TB test result is undetermined, a re-test should be performed. If the retest QuantiFERON-TB test result is undetermined, a PPD skin test should be performed. This applies for QuantiFERON®-TB test at screening as well as at EOS visit.

 The test will only be done at the end of study (EOS) visit in patients not continuing treatment in the subsequent maintenance study.

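### The end-of-treatment HBV-DNA test requires detectable DNA at screening, so core-antibody-positive, DNA-undetectable patients have no scheduled re-test

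*Protocol*

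**What the plan says.** Protocol Section 5.2.3 has two laboratory tables that mention HBV DNA.

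- **Table 5.2.3:1 (screening).** The heading is "Table 5.2.3: 1 Exclusionary testing". Its footnote 2 sets the trigger: "A HBV-DNA should be conducted if Hepatitis B core Antibody is positive and Hepatitis B Surface Antigen is negative". The same footnote then gives a "definition of occult HBV infection: B core Antibody is positive, Hepatitis B Surface Antigen is negative; HBV DNA detectable".
- **Table 5.2.3:2 (laboratory tests during the trial).** The infections row lists "HBV-DNA (quantitative) EOT Visit". Its own footnote 2 restricts this test: "HBV-DNA in case of occult HBV infection (for definition see" Table 5.2.3:1, footnote 2.

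Both Flow Charts mark hepatitis B testing at V1a only, and Section 6.2.1 places HBV blood sampling at the screening visit. Exclusion criterion 13 (Section 3.3.3.2) excludes relevant infections, including viral hepatitis, without naming HBV DNA or isolated core-antibody positivity. Section 5.2.6.1 lists HBV reactivation among the opportunistic infections that count as AESIs.

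**The concern.** The two footnotes look as if they were meant to pick out the same patients, but they do not. The EOT test is reserved for patients with detectable DNA at screening, whom criterion 13 and the table heading appear meant to keep out of the trial. Patients with past HBV exposure and undetectable DNA are not expressly excluded, although an investigator may exclude them under criterion 10 or 19. They are the group in whom a change from undetectable to detectable DNA would show reactivation, and they have no scheduled re-test.

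What is at stake is safety ascertainment, not efficacy. Without a DNA test, an AESI that has to be reported within 24 hours (Section 5.2.6.2) would come to light only through a liver-test change or an investigator's decision to look. V6 is also the handover to the extension trials. In 1368-0017, responders may be treated for up to 7 years and non-responders receive a high-dose intravenous re-induction (Section 3.1.1).

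**Working it through.** The plan states no figure on this point, so the check sets the two triggers side by side as logical conditions and looks for any other scheduled HBV-DNA test.

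**Step 1. The triggers.**

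- Screening (Table 5.2.3:1, footnote 2): core antibody positive AND surface antigen negative = 2 conditions.
- EOT (Table 5.2.3:2, footnote 2, using the definition in Table 5.2.3:1): the same 2 AND HBV DNA detectable = 3 conditions.

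**Step 2. Every case.**

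| Screening status | HBV-DNA at screening | HBV-DNA at EOT, if enrolled |
|---|---|---|
| Core antibody +, surface antigen −, DNA detectable | Yes | Yes |
| Core antibody +, surface antigen −, DNA undetectable | Yes | **No** |
| Core antibody − | No | No |
| Surface antigen + | No | No |

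The triggers differ only in the second row. For those patients the protocol text schedules 1 HBV-DNA test at screening and 0 afterwards.

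**Step 3. Any other scheduled test?** The Flow Charts, Sections 3.3.3.2, 5.2.3, 5.2.6.1 and 6.2.1, the amendment descriptions, and the protocol-deviation table and safety sections of the SAP contain no other HBV-DNA test after screening. The SAP's search for opportunistic infections (Section 7.8.1) works on reported adverse events, so it cannot find a reactivation that was never detected.

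**Step 4. What remains as monitoring.** The safety laboratory row in both Flow Charts is marked at V1a, V2, V3, V4, V5, V6 and EOS. After first dose:

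- Roll-over patients: V3 (Day 14), V4 (Day 28), V5 (Day 56), V6 (Day 84) = 4 ALT/AST draws.
- Patients not rolling over: those 4 plus EOS (Day 168) = 5 draws.

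**Step 5. Timing of the EOT result.** The last planned infusion is at V5, Day 56, and V6 is Day 84: 84 − 56 = 28 days. A V6 result cannot alter dosing in this trial. Footnote 13 of each Flow Chart makes V6 the day extension dosing starts, so for roll-over patients the result may arrive after the first extension dose.

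**The case against.** The wording gap itself is hard to dispute. The case against concerns its meaning and weight.

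- **It may be deliberate.** Criterion 13 covers relevant infections and does not name HBV DNA. If a DNA-detectable patient is enrolled, a quantitative EOT value is a sensible follow-up, and relying on liver tests in the DNA-undetectable group could be a choice. The documents do not settle this. The reading that the extra condition is misplaced rests on the table heading and the general sense of criterion 13.
- **The clinical link is not spelled out.** The protocol lists HBV reactivation without defining it and treats infection as a hypothetical class risk. That newly detectable DNA would show reactivation is a clinical premise rather than protocol text, though it follows closely from the wording of the AESI.
- **Other safeguards exist.** ALT/AST is drawn at 4 or 5 visits. Section 5.2.3 requires that "Clinically relevant abnormal laboratory test results must be confirmed using an unscheduled visit laboratory kit and should be repeated until normalization or stabilization", and "A clinically relevant value may be either in- or outside the reference range", so this rule can operate below the hepatic-injury thresholds. There are also the hepatic-injury work-up, unscheduled bloods and an external data monitoring committee. These are real but indirect: each needs a liver-test change, investigator judgement or a reported event, and the protocol text does not name HBV DNA in any of them.
- **Unseen documents may close the gap.** On the Laboratory Manual the protocol says only "Instructions regarding sample collection, sample handling/ processing and sample shipping are provided in the Laboratory Manual in the ISF". Neither that manual, the drug-induced liver injury checklist nor the extension protocols were available. Any of them might specify HBV testing.
- **The benefit is limited.** The affected group may be empty, the result comes after the last infusion, and the SAP (Section 3) records early termination, with seamless conduct of Part 2 no longer viable.

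The last two points stand and limit the practical impact. They do not remove the mismatch between the two footnotes.

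**Conclusion.** The concern holds for the protocol text as written. The EOT test carries a third condition that the screening trigger lacks, and core-antibody-positive, surface-antigen-negative, DNA-undetectable patients have no HBV-DNA test scheduled after screening (1 test, then 0). Other liver monitoring continues, so the gap is specific to HBV DNA.

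The number of patients concerned cannot be derived from the documents and may be small or zero. The conclusion assumes that the Laboratory Manual does not add the test and that some such patients are enrolled rather than excluded under criterion 10 or 19. The view that the test is aimed at the wrong patients further assumes that detectable DNA was meant to exclude. This is a worthwhile, cheap safety correction with no bearing on the efficacy analysis. Confidence is medium.

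**What to change.** Reword footnote 2 of Table 5.2.3:2 so that HBV-DNA is measured at EOT in every randomised patient who was core antibody positive and surface antigen negative at screening, whatever the screening DNA result. State that for roll-over patients the result is passed to the extension trial's investigator.

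Two optional clarifications would help: say in criterion 13 which HBV result excludes a patient, and mark the EOT test at V6 in both Flow Charts.

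The cost is one footnote, additional assays in what may be very few patients, and a handover step. V6 already has a scheduled blood draw, so no extra visit is needed; whether the existing sample suits the assay should be checked against the Laboratory Manual. The change needs amendment approval (Section 8.1) and could go into the next amendment. Given early termination, its main use would be for any patients still in the trial, for the extension handover and for any later protocol that reuses this text.

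If the Laboratory Manual already requires the test, aligning the footnote with it is enough.

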## 5.2.4 Electrocardiogram

The 12-lead ECGs will be recorded as scheduled in the flowchart. The investigator or a designee will evaluate whether the ECG is normal or abnormal and whether it is clinically relevant, if abnormal. ECGs may be repeated for quality reasons and the repeated recording used for analysis.

Additional ECGs may be recorded for safety reasons. Dated and signed printouts of ECG with findings should be documented in patient's medical record.

Clinically relevant abnormal findings will be reported either as baseline condition (if identified at the screening visit) or otherwise as adverse events and will be followed up and/or treated as medically appropriate.

